6.6 EVALUATION OF DEVICE DEFICIENCIES

Device deficiencies will be tabulated and listed in a manner similar to the methods described for adverse events. Any device deficiency leading to an adverse event or study termination will be listed separately.

7 GENERAL STATISTICAL CONSIDERATIONS

7.1 ANALYSIS WINDOWS

7.1.1 Sensor-Derived Endpoints

Participants are required to wear a Dexcom G6 sensor for 14 days prior to randomization to assess eligibility ("standard therapy" period). Current Dexcom G6 users at US sites can be exempt from this assessment period if they are willing to provide 14 days of data from their personal device from the 30 days prior to randomization.

During the 13-week randomized period, CGM data are collected continuously for both treatment arms. The period for CGM data collection is defined as follows:

Period	Start Date/Time	End Date Time
13-week randomized period	 For Intervention group: Earlier of the first non-error CGM reading using Omnipod 5, or Date/Time participant entered automated mode at Visit 3 For Control group: Noon on the day of Visit 3 	 For Intervention group: Earlier of (1) the last non- error CGM reading using Omnipod 5, on or prior to the date the Controller was returned to the site, or (2) the last non-error CGM reading using Omnipod 5 on the date of study exit visit
		 For Control group: The last CGM reading on the date of study exit visit

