10 STOPPING CRITERIA

10.1 Participant Discontinuation of Study Participation

In the case of a USADE for Intervention group participants, the Medical Monitor will determine if the use of the investigational device will be suspended while the problem is diagnosed. The use of the investigational device may continue if the Medical Monitor believes the event is explainable, unlikely to reoccur and that it is safe for the participant to continue using the device. Alternatively, the Medical Monitor may request the study participant, or all study participants, to stop using the investigational device or to only use in Manual Mode. Should Intervention group study participants be required to stop using the study device or to only use in Manual Mode due an USADE, use of the study device or Automated Mode will not be restarted until approval is received from the regulatory authorities.

Use of the investigational device by a participant will be discontinued if any of the following occur:

- The investigator, sponsor, or Medical Monitor believes it is unsafe for the participant to continue in the study for any reason. This could be due to the development of a new medical condition or worsening of an existing condition; or participant behavior contrary to the indications for use of the device that imposes on the participant's safety.
- The participant requests that the treatment be stopped
- Participant pregnancy
- Two distinct episodes of DKA as defined above
- Two distinct severe hypoglycemia events as defined above
- One episode of DKA and one severe hypoglycemia event as defined above

An additional requirement for continued study device use following a single DKA or severe hypoglycemia event will be that (1) the site investigator believes that the event is explainable, unlikely to recur, and that it is safe for the participant to continue to use the system and (2) the Medical Monitor concurs. If the Medical Monitor determines that the occurrence of the event indicates that it is not safe for the participant to continue to use the system, use will be discontinued, and the participant will be withdrawn from the study.

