7.2.3 PP (Per Protocol) Analysis Set

The Per-Protocol (PP) analysis set is a subset of the mITT analysis set. Participants will be included in the PP analysis set if they have a minimum of 80% system use as measured by the study CGM (control group) or Omnipod 5 (intervention group) during the 13 weeks over a minimum duration of 10 weeks and have completed the study without major protocol deviations. The PP analysis set will be used as supportive analysis for the endpoints. The following will be considered major protocol deviations:

- Major inclusion/exclusion criterion deviation
- Significant protocol non-compliance that may confound the study objective data (e.g., use of prohibited medications, not using control group pump for prolonged period)

The list of participants excluded from the PP analysis set will be determined prior to analysis. If the PP analysis set does not differ from the mITT analysis set, separate analyses will not be presented. If the results based on the PP analysis set different from mITT analysis differ, the per-protocol analysis should be interpreted with caution.

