7.4 CALCULATION OF PERCENTAGE OF TIME

Several effectiveness endpoints involve calculation of percentage of time in a specific glycemic range. These endpoints will be based on the direct output from a device (either a CGM or Omnipod 5). The percentage of time in a specified range (e.g., TIR) will be calculated per participant as follows:

$100 imes rac{\# of CGM readings in a specified range}{\# of evaluable CGM readings}$

The following CGM readings will be excluded from analysis, and therefore, from calculation of TIR endpoints:

- No glucose value is provided in the device output, such as due to an error or device deficiency during which the device does not record glucose readings
- CGM readings reported prior to start of the applicable period, or after the end of the applicable period (e.g., no readings prior to start of the randomized period will be included in the analysis of TIR during randomized period)

At least seven days' worth of sensor readings (168 hours, 2,016 readings) is required to calculate CGM metrics for a period. At least 126 and 42 hours' worth of sensor readings is required to calculate CGM metrics the daytime and nighttime hours, respectively. If there are insufficient data to calculate CGM metrics, the endpoints will be considered missing.

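### The Intervention CGM window ends with Omnipod 5 use while the Control window runs to study exit, so the end rule for TIR depends on the arm (minor)

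*SAP*

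**What the plan says.** SAP 7.1.1 notes that "CGM data are collected continuously for both treatment arms" and then sets a separate end rule for each arm.

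- **Intervention:** the earlier of (1) the last non-error CGM reading "using Omnipod 5, on or prior to the date the Controller was returned to the site", or (2) the last such reading on the exit-visit date. Both limbs require Omnipod 5 use.
- **Control:** "The last CGM reading on the date of study exit visit". The participant's pump is not mentioned.

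SAP 7.4 excludes "CGM readings reported prior to start of the applicable period, or after the end of the applicable period". SAP 7.6.1 treats a participant with at least seven days of readings (2,016) as having an observed value, formed from all available readings in the window. SAP 7.2.2 makes the mITT set, meaning everyone randomized, the primary set. Prolonged non-use of the Control pump appears only as a per-protocol deviation in SAP 7.2.3.

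On the data source, SAP 7.4 says: "These endpoints will be based on the direct output from a device (either a CGM or Omnipod 5)". SAP 3.1 names the study CGM as the measuring device, and Protocol 13.2.2 says that data from the CGM device are collected for all participants.

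Protocol 10.1 covers stopping the device. After a USADE, one or all Intervention participants may be told to stop using it, and "use of the study device or Automated Mode will not be restarted until approval is received from the regulatory authorities". Only where the Medical Monitor judges continued use unsafe after a DKA or severe hypoglycemia event does the section add that "use will be discontinued, and the participant will be withdrawn from the study".

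**The concern.** For anyone who leaves Omnipod 5 before exit and keeps wearing the study sensor, the endpoint measures different things in the two arms: glucose up to device stop in Intervention, and glucose up to study exit in Control. A Control participant who changes or abandons the pump contributes to the end. That does not fit a comparison of all randomized participants over 13 weeks.

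If glucose worsens after the device is stopped, the rule favours the device on TIR, time above 180 mg/dL and mean glucose. For time below 54 and below 70 mg/dL the direction is not established. TIR is the endpoint that alone defines study success (SAP 2.4). Where the SAP and protocol differ the SAP prevails (SAP 1, Protocol 12.7), so the percentage-of-time formula in Protocol 12, which has no device condition, does not override the rule.

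**Working it through.** **1. How the rule works.** Take an Intervention participant who stops Omnipod 5 mid-period, does not restart, and wears the study G6 until exit. No Omnipod 5 reading exists on the exit date, so limb (2) is empty and limb (1) ends the window at the last Omnipod 5 reading. SAP 7.4 then drops the rest. Manual Mode readings are still taken on Omnipod 5 and count. If use restarts before exit, the end rule cuts nothing.

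**2. Whether planned analyses would show it.** The threshold is 7 x 288 = 2,016 readings, or 7/91 = 7.7% of the period. Above it:
- complete-case analysis (SAP 4.3.1) keeps the shortened value;
- multiple imputation (4.3.2) does not touch it;
- tipping-point shifts (4.3.3) apply only to imputed values;
- the per-protocol set may remove the person but does not restore the readings.

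Change in A1C has no device condition (SAP 5.1.4, 7.1.2), so it reflects time off the device, but only as an indirect check.

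**3. The plan's own sample size.** Inputs (SAP 4.1): difference 10, SD 16.5, two-sided 5%, power 90%, 2:1. The normal approximation gives 43 Control and 129 in total; noncentral-t power at 87/44 is 90.2%. The stated 131 is reproduced. Attrition: 200 x 0.85 = 170; 170 x (1 - 0.229) = 131.07.

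**4. Size of the overstatement.** Let *f* be the share of Intervention participants who stop and stay under CGM, *r* the share of the period left, and *L* the TIR loss after stopping. With even sensor coverage, a stopper's value is too high by *r* x *L*, and the arm mean by *f* x *r* x *L*.

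- *f*: not in the documents. Assumed 2-10%; 170 x 2/3 = 113, so about 2 to 11 people.
- *r*: not in the documents. Assumed 0.5.
- *L*: Protocol 1 reports TIR of 74.4% in the first automated phase and 65.5% in Manual Mode, a fall of 8.9, and expects 8-12 points of benefit from the algorithm. These figures describe Manual Mode; applying them to leaving the device is a further assumption.

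| Case | *f* = 2% | *f* = 10% |
|---|---|---|
| *L* = 8 | 0.02 x 0.5 x 8 = 0.08 | 0.10 x 0.5 x 8 = 0.40 |
| *L* = 8.9 | 0.02 x 0.5 x 8.9 = 0.09 | 0.10 x 0.5 x 8.9 = 0.45 |
| *L* = 12 | 0.02 x 0.5 x 12 = 0.12 | 0.10 x 0.5 x 12 = 0.60 |
| Stoppers gained half (*L* = 4.45) | 0.04 | 0.22 |
| Stoppers gained nothing (*L* = 0) | 0 | 0 |

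Timing check: stopping just after day 7 gives *r* = 84/91 = 0.923, and the largest corner becomes 0.10 x 0.923 x 12 = 1.11.

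**5. Comparator.** With all 170 randomized (113/57) and no covariate adjustment, SE = 16.5 x sqrt(1/113 + 1/57) = 2.68, and the smallest significant difference is 1.974 x 2.68 = 5.29. Then 0.60/5.29 = 11%. A difference of 10 - 0.60 = 9.40 still lies well above 5.29.

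**The case against.** The strongest reply is that the affected participant may hardly exist. The protocol has no schedule for follow-up off the device. Table 1 and Protocol 7.7 and 7.9 place Omnipod 5 return and the end of CGM collection at the same visit, where the two end rules nearly agree. The device-stop list in Protocol 10.1 sits under a heading about ending study participation. This stands as a limit on frequency. It does not close the gap, because the list itself does not state withdrawal and the USADE paragraph allows a device stop without it.

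A second reply is that the wording on Omnipod 5 use may only describe where Intervention CGM data come from. Protocol 13.2.1 exports CGM data through the Omnipod 5 System, and Visit 3 confirms CGM transmission for Control only. That is a fair reading, and it is why an independent G6 record must be confirmed. It does not make the rule equal between arms.

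Three stronger readings are tempting and not supported:

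- A reader might infer from limb (1) that the SAP foresaw off-device follow-up. Ordinary data cuts explain it equally well: no reading on the exit date, a Controller returned earlier, or loss to follow-up.
- A reader might take the 22.9% attrition allowance as the stopping rate. That figure is for people not completing the 13 weeks, not for people who stop the device and stay under CGM.
- A reader might carry over the 23% who used another regimen in the earlier trial's pause. That would need a trial-wide suspension here, beginning mid-period and not lifted before exit, for which the documents give no basis.

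**Conclusion.** The concern holds as a minor point. The end rule differs by arm in an all-randomized analysis, can drop Intervention glucose after device stop, and is not exposed by any planned TIR sensitivity analysis. Under the assumptions shown (2-10% stopping, half the period left, a loss of 8-12 points), the TIR difference is overstated by about 0.08-0.60 points; it is zero if stoppers had gained nothing from the device. Neither the rate, the timing nor the loss off-device is given in the documents.

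A reader might infer that the rule could produce a positive primary result by itself. The figures do not support that: the overstatement is small beside the 10-point design difference and the 5.3-point threshold. The case for acting is that the asymmetry is avoidable and cheap to remove.

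**What to change.** In SAP 7.1.1, use one window end for both arms: the last study-G6 reading on or before the study exit date, whatever insulin device is in use. Take it from the CGM device data described in Protocol 13.2.2, name that source in SAP 7.4, and apply it in the same way to both arms. Do not fill Intervention gaps from a second source, which would create a new arm-specific rule.

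Keep the window bounded by Omnipod 5 use as a supportive analysis. Report how many Intervention participants, and how many days, fall between device stop and exit.

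The cost is SAP wording, some data handling, and confirmation that the Intervention G6 record is captured independently of Omnipod 5. Protocol 13.2.2, the Dexcom app requirement in the inclusion criteria and the instruction in Protocol 7.3.1 to use only the study G6 suggest that it should be. The estimate may become slightly less favourable to the device.

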7.1.2 Other Endpoints

For A1C, PROs, and BMI, baseline is defined as the value collected prior to randomization (at Visit 1 or 3). The analysis window for the 13-week timepoint is as follows:

		Analysis Window	
Timepoint	Target Date	A1c/BMI	PROs
13 Week	Study day 90	± 2 weeks	± 5 weeks

If a measurement was collected within analysis window, and has been attributed to Visit 8 (13 weeks), then that measurement will be used in the analysis of the endpoint. Otherwise, the measurement within the analysis window that is closest to the indicated target date will be used for analysis. If no measurement is available within the analysis window, the endpoint will be treated as missing.

7.2 ANALYSIS SETS

The following analysis sets are planned for the study (Period 1 only):

7.2.1 ITT (Intention to Treat) Analysis Set

The ITT analysis set includes all participants that are enrolled in the study.

7.2.2 mITT (modified Intention to Treat) Analysis Set

The modified Intention to Treat (mITT) analysis set is a subset of the ITT analysis set. The mITT analysis set will consist of all participants who have been randomized. The mITT analysis set will be used as the primary analysis for the primary and secondary endpoints, as well as safety analyses, and for other clinical outcome data.

7.2.3 PP (Per Protocol) Analysis Set

The Per-Protocol (PP) analysis set is a subset of the mITT analysis set. Participants will be included in the PP analysis set if they have a minimum of 80% system use as measured by the study CGM (control group) or Omnipod 5 (intervention group) during the 13 weeks over a minimum duration of 10 weeks and have completed the study without major protocol deviations. The PP analysis set will be used as supportive analysis for the endpoints. The following will be considered major protocol deviations:

- Major inclusion/exclusion criterion deviation
- Significant protocol non-compliance that may confound the study objective data (e.g., use of prohibited medications, not using control group pump for prolonged period)

The list of participants excluded from the PP analysis set will be determined prior to analysis. If the PP analysis set does not differ from the mITT analysis set, separate analyses will not be presented. If the results based on the PP analysis set different from mITT analysis differ, the per-protocol analysis should be interpreted with caution.

7.3 CONTROL OF SYSTEMATIC BIAS

Several measures are incorporated into the study design to help minimize study bias as follows:

- This is a randomized, multi-center study to help ensure that investigator or site or participant enrollment bias is minimized. Selection of participants will be made from the Investigator's usual participant load. Consecutively eligible participants should be enrolled into the study.
- 2) This document specifies appropriate statistical methodology to ensure that bias is minimized.
- 3) The effectiveness measures will be based on the direct output from the device or are analyzed at a NGSP certified central laboratory, ensuring objective reporting.
- 4) A Medical Monitor will adjudicate all SAEs and device-related adverse events to ensure consistency across all evets; the Medical Monitor's assessment of adverse events will be used for regulatory reports, product labeling, and publications or presentation.

7.4 CALCULATION OF PERCENTAGE OF TIME

Several effectiveness endpoints involve calculation of percentage of time in a specific glycemic range. These endpoints will be based on the direct output from a device (either a CGM or Omnipod 5). The percentage of time in a specified range (e.g., TIR) will be calculated per participant as follows:

$100 imes rac{\# of CGM readings in a specified range}{\# of evaluable CGM readings}$

The following CGM readings will be excluded from analysis, and therefore, from calculation of TIR endpoints:

- No glucose value is provided in the device output, such as due to an error or device deficiency during which the device does not record glucose readings
- CGM readings reported prior to start of the applicable period, or after the end of the applicable period (e.g., no readings prior to start of the randomized period will be included in the analysis of TIR during randomized period)

At least seven days' worth of sensor readings (168 hours, 2,016 readings) is required to calculate CGM metrics for a period. At least 126 and 42 hours' worth of sensor readings is required to calculate CGM metrics the daytime and nighttime hours, respectively. If there are insufficient data to calculate CGM metrics, the endpoints will be considered missing.

7.5 LENGTH OF RANDOMIZED PERIOD

For certain analyses, it may be necessary to calculate the length of the randomized period. The length of randomized period is calculated as the difference between the start of the randomized period and the end of the randomized period. The start and end of the randomized period for sensor-derived endpoints for each treatment group is described in Section 7.1.1 of this document. For other analyses and summaries, the length of randomized period is calculated (in days) as date of Visit 8 (Study Exit) minus date of Visit 3, +1.

7.6 MISSING DATA HANDLING (PERIOD 1 ONLY)

7.6.1 Missing Data Handling for Sensor-Derived Endpoints

The primary endpoint of TIR 70-180 mg/dL during the 13-week randomized period will be considered missing for any participant with less than 7 days' worth of sensor readings (equal to 2,016 readings).

Due to the nature of the data and study design, it is anticipated that all randomized participants will contribute at least some sensor data post-randomization. Hence, it is possible that there will be no need for imputation of missing values for these endpoints. All randomized participants (i.e., mITT analysis set) will provide an endpoint value for the primary endpoint and all secondary sensor-derived endpoints as follows:

• If a randomized participant provides at least seven days' worth of sensor readings (2,016 readings) during the randomized period, all the available sensor readings will be collapsed (averaged) for a per-participant value for a specific CGM-derived endpoint.

• If a randomized participant does not provide at least seven days' worth of sensor readings (2,016 readings) during the randomized period, the sensor readings for that participant will be excluded from analysis, and instead, a per-participant value for a specific CGM-derived endpoint will be imputed.

Gaps in sensor data, such as due to loss of signal, will not be imputed as imputing single sensor readings data points is clinically inappropriate and would render single CGM data imputation clinically not meaningful.

Because there are numerous reasons that data may be missing for patients in a clinical trial and the methods for handling missing data makes a number of untestable assumptions, sensitivity analyses will be performed to explore (1) whether results are similar for the primary analysis when using different methods and (2) to evaluate the impact of deviations from missing at random (MAR) and missing completely at random (MCAR) assumptions for the primary endpoint.

7.6.1.1 Missing Data Handling for A1C- and PRO-Derived Endpoints

It is likely that at least some participants do not contribute data for A1c, BMI, or Patient-Reported Outcomes (PROs) (e.g., due to early withdrawal). For the main analysis of such endpoints, missing values for the participants in the mITT analysis set will be imputed as follows:

- If a participant withdrew from the study early and provided an endpoint value collected within 13-week analysis window (Section 7.1), the last known value will be used in the analysis of the endpoint.
- If a participant is confirmed to have withdrawn early from the study due to unsatisfactory treatment or potential loss of efficacy outside of the analysis window (Section 7.1), the change from baseline in a specific endpoint will be assumed to be zero (e.g., no change).
- If a participant does not provide a value for the specific endpoint for other reason (e.g., lost sample, participant lost to follow-up), the endpoint data will be imputed.

This allows for all participants in the mITT analysis set to be included in the analysis of these endpoints.

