7.9 Early Withdrawal

Any participant may withdraw from the study at any time for any reason. Upon withdrawal, assessments will be performed following Table 1: Schedule of Assessments and Table 2: Patient Reported Outcomes (Questionnaires). The investigator may also terminate a participant's participation in the study if it is in the best interest of the participant or if the Sponsor or local regulatory agency terminates the study.

The Early Withdrawal visit will include:

- A1C (central laboratory)
- Review of concomitant medications
- Weight
- Vital signs
- Assessment of AEs
- Insulin delivery metrics (e.g., TDI, average basal and bolus insulin dose, and time on device) (Control group only)
- Completion of questionnaires (Table 2: Patient Reported Outcomes (Questionnaires))
- Return BG meter, Ketone meter, and study CGM, if unused
- Return Omnipod 5 System (Intervention group only)
- Stop CGM data collection
- Data Portal discontinuation (Intervention group only)
- Complaints/device deficiencies such as occlusion alarms and system hazard alarms since last visit
- BG/ketone meter data review by clinician
- Pump and CGM data review by clinician

The reason for withdrawal will be recorded, and their participation in the study will end.

In the event of a participant's death during the study, the participant's participation will be considered terminated, and the date of death will be used as the date of study exit.

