12.6 Missing Data

All practical monitoring and follow-up steps will be taken to ensure complete and accurate data collection.

Due to the nature of the data and study design, it is anticipated that all randomized subjects will contribute some CGM data post-randomization. Hence, it is possible that there will be no need for imputation of missing values for the CGM endpoints. A subject will be included in analysis of CGM endpoints in the mITT analysis set only if the subject provides at least seven days' worth of sensor readings during the course of 13 weeks. This is equivalent to 2016 readings, assuming CGM readings are taken at approximately every five minutes for a total of 288 readings per day. No additional imputations for missing data are planned for the primary endpoint, and secondary endpoints involving CGM data. Missing records (i.e. gaps in data) will not be imputed for either the intervention or control group.

CGM values for other reasons will not be imputed.

It is likely that at least some subjects do not contribute data for the A1C and patient-reported outcome endpoints (e.g., due to early withdrawal).

For the main analysis of A1C and patient-reported outcomes, missing values for the subjects in the mITT analysis set will be imputed using the subject's last known A1C/ePRO value if collected within the analysis window (such as during Early Withdrawal visit). The analysis windows are assigned as follows:

- A1C à 13±2 weeks from start of the 13-week randomized period
- PROs à 13±5 weeks from start of the 13-week randomized period

Questionnaire scoring will follow the scoring guidelines; PRO scores either at baseline or at 13 weeks that are missing for other reasons (e.g., due to unanswered questions) will not be imputed. No imputation for missing data will be included in the analyses based on Per Protocol analysis set. Additional sensitivity analyses will be detailed in the SAP.

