4 ANALYSIS OF PRIMARY ENDPOINT

4.1 SAMPLE SIZE

The sample size estimation is based on the following assumptions:

- Power of 90% and two-sided significance level of 5%
- Difference between groups of 10% in TIR 70-180 mg/dL
- Standard deviation of 16.5% in each group
- 2:1 randomization (Intervention:Control)

Under these assumptions, a total sample size of 131 participants is required (87 Intervention, 44 Control). To allow for pre-randomization attrition of up to 15%, and post-randomization attrition of up to 22.9%, a total sample size of up to 200 will be enrolled to give 170 participants randomized and 131 participants completing the 13 weeks. The anticipated difference in TIR 70-180 mg/dL was projected from the OP5 pivotal study.

The sample size calculations were performed using PASS 2021.

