5 ANALYSIS OF OTHER ENDPOINTS

5.1 ANALYSIS OF SECONDARY ENDPOINTS (PERIOD 1)

To preserve the family-wise type 1 error for selected key secondary endpoints, a fixed sequence hierarchical testing approach will be used. If the primary endpoint is found to be statistically significant at a two-sided significance level of 5%, testing for secondary endpoints can commence. Secondary endpoints will be tested in a hierarchical fashion at a one-sided significance level of 2.5% (or two-sided significance level of 5% as appropriate). Each endpoint with a two-sided p-value ≤ 0.05 (or one-sided p-value of ≤ 0.025 , as appropriate) is considered to be met until a secondary endpoint with a two-sided p-value ≥ 0.05 (or one-sided p-value of ≥ 0.025 , as appropriate) is encountered. This process continues iteratively moving to the next endpoint down on the list until a non-significant result is observed, or all endpoints have been tested. If a non-significant result is encountered, then formal statistical hypothesis testing is terminated and any variables below on the list are not formally tested.

Regardless of the results of the hierarchical testing, summary statistics appropriate to the distribution will be tabulated for each key secondary endpoint by treatment group. A 95% confidence interval for the treatment effect will also be calculated for all key secondary outcomes listed above. However, a confidence interval that is below zero (superiority) or that is below the non-inferiority margin (noninferiority) will not be considered a statistically significant result if an outcome variable higher on the hierarchical list failed to reach statistical significance.

The secondary endpoints will be analyzed using a repeated measures linear mixed effects model with the endpoint at baseline and at 13 weeks as the dependent variable. The correlation between baseline and follow-up will be modelled using an unstructured covariance matrix. The model will include randomized treatment group, age, sex, and duration of diagnosis as fixed effects and site as a random effect. This model adjusts for baseline value of the endpoint by forcing the treatment groups to have the same mean value at baseline. Missing data will be handled by using a direct likelihood approach which will allow participants to be included even if they only have data at one of the time points.

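### SAP 5.1 and SAP 7.6.1.1 give incompatible main missing-data methods for change in A1C, T1-DDS, HCS and DQOL-brief, and the zero-change rule in 7.6.1.1 can attenuate or bias the comparison

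*SAP*

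**What the plan says.** **SAP 5.1** fits a repeated measures mixed model to baseline and 13 weeks for the continuous secondary endpoints: "Missing data will be handled by using a direct likelihood approach which will allow participants to be included" even with only one of the two time points. Nothing is filled in. SAP 4.2 states that this approach assumes data missing at random.

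**SAP 7.6.1.1** says that, for the main analysis of A1C, BMI and PROs, missing values in the mITT set are imputed by three rules:

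1. An early withdrawal with a value inside the 13-week window keeps that value.
2. For a participant confirmed to have left because treatment was unsatisfactory or efficacy may have been lost, outside the window, "the change from baseline in a specific endpoint will be assumed to be zero (e.g., no change".
3. A value missing for any other reason is imputed. No method is named.

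The section adds that all mITT participants can thereby be included.

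**SAP 7.1.2** sets the window at day 90 ± 2 weeks for A1C and BMI and ± 5 weeks for PROs. An endpoint with no measurement in the window is missing.

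**Protocol 12.6** uses the "last known A1C/ePRO value if collected within the analysis window" and has no zero-change rule. **Protocol 7.9** collects central-laboratory A1C and the questionnaires at the Early Withdrawal visit. Protocol 12.7 and SAP 1 give the SAP precedence over the protocol.

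**The concern.** Change in A1C, T1-DDS, HCS and DQOL-brief (SAP 5.1.4 and 5.1.6 to 5.1.8) are tested in a fixed sequence, where one failure stops all later tests. Two programmers following different sections of the same SAP could get different estimates and p-values, and so stop at different points.

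The zero rule also raises questions of its own:

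- It enters an assumed value as though it had been observed. That targets a different quantity from the one in 5.1, and the SAP does not say so.
- Its trigger is a confirmed reason for leaving, but neither document says who confirms it or by what criteria. Participants know which device they use, so the stated reasons may differ by arm.
- No sensitivity analysis tests it. Protocol 12.6 leaves additional sensitivity analyses to the SAP, and SAP 4.3 and 7.6.1 define them for the primary endpoint only.

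**Working it through.** **1. The plan's own figures.** The documents give no number for this rule. The only sample size is for TIR (SAP 4.1): "Difference between groups of 10% in TIR 70-180 mg/dL", "Standard deviation of 16.5% in each group", 2:1 allocation, two-sided 5%, 90% power. The normal approximation gives 43 + 86 = 129. The noncentral t-test gives power 0.9018 with 87 and 44, and 0.8974 with 87 and 43, so 131 reproduces. Attrition also reproduces: 200 × 0.85 = 170, and 170 × (1 − 0.229) = 131.07. The 170 randomised, split 2:1, give the 113 and 57 used below.

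**2. Are the two methods compatible?** Direct likelihood acts on outcomes left missing. Once rules 1 to 3 have run, none are left. The methods are therefore alternatives and cannot be applied in sequence.

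**3. No true change.** Let a fraction q of an arm of size n be set to zero, with change SD s and mean change 0.

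- Zero-filled mean: variance of change (1−q)s², so SE = s√((1−q)/n).
- Complete data only: SE = s/√((1−q)n).
- Ratio: 1−q.

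The zero-filled SE is smaller, but the estimate itself is also scaled by (1−q). Its true sampling SD is the same s√((1−q)/n), so the test keeps its size.

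Simulation inputs: 113 vs 57 participants and 4,000 runs per scenario; SDs 0.86 (baseline) and 0.68 (13 weeks), from the earlier single-arm study in Protocol 1; correlation 0.7 (assumed); withdrawal at random (assumed). ANCOVA on baseline stands in for the mixed model, and complete-case ANCOVA for direct likelihood. At q = 10%, the model SE was 0.0773 against an actual SD of 0.0777. Across scenarios with no change in either arm, the zero-rule type I error was 0.048 to 0.053.

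**4. A true effect, equal shares.** Changes here are 13 weeks minus baseline, so a fall is negative; SAP 5.1.4 writes A1C change the other way round. If only Intervention changes, by c, its zero-filled mean is (1−f)c. With c = −0.38 (the within-group fall in the earlier study, borrowed as an illustrative effect):

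| Share zero-filled, both arms | (1−f) × (−0.38) | Simulated mean, zero rule | Simulated mean, direct likelihood | 95% CI coverage of −0.38, zero rule |
|---|---|---|---|---|
| 5% | −0.361 | −0.359 | −0.378 | 94% |
| 10% | −0.342 | −0.341 | −0.379 | 92% |
| 22.9% | −0.293 | −0.296 | −0.383 | 81% |

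The last row is only a ceiling. It puts all planned attrition, whatever the reason or timing, under the zero rule.

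**5. Both arms change, unequal shares.** With a common change c and no true difference, the zero-filled difference is (1−fI)c − (1−fC)c = −(fI − fC)c.

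- fI = 2%, fC = 10%, c = −0.38: −(0.02 − 0.10)(−0.38) = −0.0304, in favour of the device.
- With an SE of about 0.079, the shift is 0.0304/0.079 = 0.385 SE.
- Type I error ≈ Φ(−1.96 + 0.385) + Φ(−1.96 − 0.385) = 0.0576 + 0.0095 = 0.067.

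Reversing the shares reverses the bias, with the same approximate error rate.

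**The case against.** **Zero change is a recognised strategy.** Giving no benefit to people who leave because treatment failed can be a deliberate prespecified choice. Direct likelihood instead assumes that they would have resembled completers given baseline, which may be less cautious. This stands as an argument for declaring the estimand. It does not remove the conflict with 5.1.

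**Attenuation works against the sponsor.** True when the shares are equal or when only Intervention improves. It does not cover step 5, where both arms improve and more Control participants leave for this reason.

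**Few participants may be affected.** Probably so. The rule needs a confirmed reason and a withdrawal outside the window, whereas the 22.9% covers all reasons.

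**The wording of rule 3 may be loose.** "Imputed" could be shorthand for the likelihood method, or could refer to the multiple imputation that 5.1 reserves for its robust-regression fallback. Either reading might rescue rule 3. Neither rescues rule 2, which assigns an explicit value.

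Two stronger readings are tempting and do not hold. A reader might infer that filling with a constant makes the SE too small and so inflates type I error. The SE is smaller than under direct likelihood, but it is correct for the zero-filled estimator, and size is kept when neither arm changes (step 3). A reader might also infer that any A1C or questionnaire measured at withdrawal is discarded for a zero. Rule 1 keeps values inside the window, and SAP 7.1.2 already makes values outside it missing, so direct likelihood as written would not use them either.

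**Conclusion.** The point holds as a contradiction inside the SAP on four hierarchically tested endpoints, together with an undeclared and untested zero-change rule. It should be corrected, though it does not touch the primary endpoint.

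The effect on estimates is modest at plausible shares. A difference of −0.38 becomes about −0.34 with 10% zero-filled in each arm. With a common change of −0.38 and shares of 2% and 10%, the bias is about 0.03 in size and type I error about 0.07. The contradiction itself rests on the text alone. The sizes rest on assumptions: the affected share, the correlation of 0.7, withdrawal at random, and A1C figures from an earlier study with mean baseline A1C 7.16%, whereas this trial requires at least 80% of participants at 8% or above. Steps 4 and 5 scale in proportion to the change, so larger changes give larger distortions. No corresponding size can be given for the questionnaires, because the documents give no SD for them.

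**What to change.** State one main method for the A1C and questionnaire endpoints, in the same terms in SAP 5.1 and 7.6.1.1.

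- **Preferred:** keep direct likelihood as in 5.1. Remove the zero-change rule and the unspecified imputation rule from the main analysis, and keep the rule that uses in-window withdrawal values. Report two sensitivity analyses: zero change for the withdrawals now named in 7.6.1.1, and measured early-withdrawal values regardless of window. Tabulate by arm how many participants each affects.
- **Alternative:** if zero change is meant as a treatment-failure estimand, declare it, define who confirms the reason and by what criteria, name the method for other missing values, and amend 5.1 to match.

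The cost is SAP wording and one sensitivity table, with no new data collection. Under the preferred option, intervals are slightly wider than with zero-filling: in the illustration, an SE of 0.083 against 0.077 to 0.079 at a 10% share.
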